## 11.4 Subgroup analyses

Subgroup analyses are planned to explore a possible heterogeneity of the treatment effect concerning the following baseline characteristics: setting (outpatients versus hospitalized patients), gender, age (< 65 versus  $\geq 65$  years), kidney function (eGFR  $\geq 30$  mL/min/1.73m^2 and < 50 mL/min/1.73m^2 versus eGFR  $\geq 50$  mL/min/1.73m^2), smoking status, diabetes, presence of coronary heart disease or heart failure (yes/no), need for oxygen treatment at baseline (supplementary oxygen required versus not required), inclusion based on D-dimer, hs-cTnT or both. For subgroup analyses the respective baseline characteristic and its interaction with treatment are included in the regression models described above for the primary and secondary endpoints. Treatment effect heterogeneity across subgroups will also be visually inspected in forest plots.

## 11.5 Safety Endpoints

Safety analyses will follow standard procedures for the reporting of adverse events; these will be reported as frequencies (percentages) by treatment group. All safety analyses will be based on the safety set. One safety endpoint of particular interest are bleeding events (see Section 9.3.1). The time to bleeding events will be analyzed in a Cox proportional hazards model, if a sufficient number of events will be observed. Treatment group differences will be reported as hazard ratios with 95% confidence intervals and p-values testing the null hypothesis of no group difference (i.e. HR=1). The estimation of the probability for bleeding events will account for competing events such as death and premature study discontinuation using the Aalen-Johansen estimator, the so-called cumulative incidence function.

Differences between treatment groups in continuous laboratory parameters and vital signs over follow-up time will be explored in longitudinal box plots.

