The MARINER study was then designed to improve the overall safety of medically ill patients with rivaroxaban treatment for 45 days post hospital discharge by addressing the bleeding risk observed in the MAGELLAN study. The MARINER patients exhibited a higher VTE-risk than those in MAGELLAN to enhance the overall expected benefit/risk assessment (22). The VTE-risk in the patients from the MARINER Study was more than 2,9% annually according to the IMPROVE Score. The study did not show a benefit in reducing the risk of the composite endpoint (VTE and VTE related death) in acute medically ill patients following hospital discharge. However, when examining VTE only, fewer events were observed in the group treated with rivaroxaban. The incidence of major bleeding in both study arms was low.

According to the actual literature, patients with COVID-19 present a much higher incidence of thrombotic complications than those included in the MARINER study, even with prophylactic anticoagulation (12, 14). Therefore, COVID-PREVENT was designed to determine whether the use of rivaroxaban at a dose of 20mg OD combined with a thromboprophylaxis dose of 10mg OD post discharge reduces fatal or nonfatal thromboembolic and cardiovascular events in comparison to SOC with prophylactic LMWH or UFH in patients with moderate to severe COVID-19.

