## 5. TREATMENT ALLOCATION AND BLINDING

### Treatment Allocation

#### Procedures for Randomization and Stratification

This trial is an open label study. Central randomization will be implemented in this study. Subjects will be randomly assigned to 1 of 2 treatment groups (rivaroxaban or SOC with prophylactic UFH or LMWH) in a 1:1 fashion based on a computer-generated randomization schedule prepared before the study starts under the supervision of the sponsor. Randomization will follow a dynamic randomization algorithm with residual randomness designed to minimize imbalance in terms of variance between treatments taking the following stratification factors into account: site, gender (male, female, diverse), age (< 65 versus  $\geq$  65 years), kidney function (eGFR  $\geq$  30 mL/min/1.73m^2 and < 50 mL/min/1.73m^2 versus eGFR  $\geq$  50 mL/min/1.73m^2), history of CAD or heart failure (yes/no), oxygen demand on admission to the hospital (supplementary oxygen required versus not required) and setting (outpatients versus hospitalized patients). The computer system will dictate the treatment assignment for the subject. The requestor must use his or her own user identification and personal identification number when contacting the system and will then give the relevant subject details to uniquely identify the subject.

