### **9.3. Safety Evaluations and Endpoints**

#### **9.3.1. Bleeding Events**

The study will include the following evaluations of safety and tolerability according to the time points provided in the TIME AND EVENTS SCHEDULE: ISTH fatal or non-fatal major bleeding, non-major clinically relevant bleeding, other non-major bleeding that lead to study drug interruption for more than 7 days, adverse events, and clinical laboratory tests.

The study will use the ISTH Bleeding Event Classification Scale to assess bleeding events as major, non-major clinically relevant bleeding, or other bleeding. Similar to efficacy endpoint, the same independent CEC will adjudicate and classify bleeding events according to definitions in the CEC charter.

The principal safety endpoint for this study is fatal or non-fatal major bleeding using validated ISTH bleeding criteria (27). Other safety endpoints are non-major clinically relevant bleeding and non-major bleeding that lead to study drug interruption for more than 7 days.

An ISTH major bleeding event is defined as overt bleeding that is associated with:

- A fall in hemoglobin of 2 g/dL or more, or
- A transfusion of 2 or more units of packed red blood cells or whole blood, or
- A critical site: intracranial, intraspinal, intraocular, pericardial, intra-articular, intramuscular with compartment syndrome, retroperitoneal, or
- A fatal outcome

Non-major clinically relevant bleeding is defined as overt bleeding not meeting the criteria for major bleeding but associated with medical intervention, unscheduled contact (visit or telephone call) with a physician, (temporary) cessation of study treatment, or associated with discomfort for the subject such as pain or impairment of activities of daily life. Examples of non-major clinically relevant bleeding are:

- Epistaxis if it lasts for more than 5 minutes, if it is repetitive (i.e. 2 or more episodes of true bleeding, i.e. not spots on a handkerchief, within 24 hours), or leads to an intervention (packing, electrocautery, etc.)
- Gingival bleeding if it occurs spontaneously (i.e. unrelated to tooth brushing or eating), or if it lasts for more than 5 minutes
- Hematuria if it is macroscopic, and either spontaneous or lasts for more than 24 hours after instrumentation (e.g. catheter placement or surgery) of the urogenital tract
- Macroscopic gastrointestinal hemorrhage: at least 1 episode of melena or hematemesis, if clinically apparent

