## 11.7 Sample size determination

Sample size calculation is based on the primary endpoint D-dimer at day 7 corrected for baseline values. Since the distribution of D-dimer concentrations is skewed, calculations are done on the log scale. Using an analysis of covariance (ANCOVA) (significance level  $\alpha=0.05$  two-sided) with baseline values as covariate a total sample size of 80, i.e. 40 per group, gives a power of 80% to detect a mean difference of 0.44 (on the log scale) between the treatment group and the control group at day 7. Based on a blinded review, a common standard deviation of SD=0.8 and a correlation to baseline of  $r=0.5$  (both on the natural log scale) were assumed. The effect assumed translates to a reduction of 36% in D-Dimer values on the original scale. The co-primary endpoint is a seven-category ordinal scale previously recommended by the WHO (Attachment 2) as clinical improvement scale for patients with respiratory infections. Here 40 patients per group will give a power of 80% to detect a relative treatment effect  $p_1=0.68$  between treatment and control group at day 7 using a Wilcoxon (Mann-Whitney) rank-sum test (two sided,  $\alpha=0.05$ ). The probabilistic index or relative effect  $p_1$  denotes the probability that an observation in the treatment group will be less than an observation in the control group. Targeting a total of at least 80 evaluable patients, we aim to recruit about 100 patients.

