
11.7 sample size determination
	
Sample size calculation is based on the primary endpoint D-dimer at day 7
	
As mentioned above, the endpoints were changed which also lead to an

	
corrected for baseline values. Since the distribution of D-dimer concentrations is skewed, calculations are done on the log scale. Using an analysis of covariance (ANCOVA) (significance level alpha=0.05 two-sided) with baseline values as covariate a total sample size of 80, i.e. 40 per group, gives a power of 80% to detect a mean difference of 0.44 (on the log scale) between the treatment group and the control group at day 7. Based on a blinded review, a common standard deviation of SD=0.8 and a correlation to baseline of r=0.5 (both on the natural log scale) were assumed. The effect assumed translates to a reduction of 36% in D-Dimer values on the original scale. The co-primary endpoint is a seven-category ordinal scale previously recommended by the WHO (Attachment 2) as clinical improvement scale for patients with respiratory infections. Here 40 patients per group will give a power of 80% to detect a relative treatment effect <math>p_1=0.68</math> between treatment and control group at day 7 using a Wilcoxon (Mann-Whitney) rank-sum test (two sided, alpha=0.05). The probabilistic index or relative effect <math>p_1</math> denotes the probability that an observation in the treatment group will be less than an observation in the control group. Targeting a total of at least 80 evaluable patients, we aim to recruit about 100 patients.
 
A total of 120 primary endpoint events yields a power of 80% at a two-sided significance level of 5% given a hazard ratio of 0.60, i.e. a reduction of 40% in terms of hazards for the primary endpoint, and 1:1 randomization (Schoenfeld formula). This event driven study is completed once 120 events are observed. The sample size per group is then given depending on the proportion of patients in the control group having at least one primary endpoint event:
	
adaptation of the sample size. Based on the new primary endpoint D-dimer on day 7 a new sample size was calculated. The aim is now to close the study with approximately 100 patients. This sample size is also sufficient for the new „co-primary“ endpoint „seven-category ordinal scale“.
 
111 patients have been randomized into the study until the trial has been set on-hold on June 11, 2021. After the proposed amendment has been evaluated by the regulatory authorities, it is planned to stop the study without recruiting additional patients into the study.

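### Bleeding is compared between arms only by a conditional Cox hazard ratio, which at about 50 patients per arm and major-bleeding risks of about 2% or less will more likely than not be inestimable

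*Protocol*

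**What the plan says.** The safety objective in Section 2.1 is comparative: bleeding on rivaroxaban against bleeding on standard of care, up to day 35. Section 9.3.1 ranks the endpoints: "The principal safety endpoint for this study is fatal or non-fatal major bleeding using validated ISTH bleeding criteria". Clinically relevant non-major bleeding, and non-major bleeding with a long interruption of study drug, come after it.

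Section 11.5, repeated in the Synopsis, provides three outputs for the safety set:

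- adverse event frequencies and percentages by arm;
- the probability of bleeding by the Aalen-Johansen estimator, with death and premature study discontinuation as competing events;
- a regression: "The time to bleeding events will be analyzed in a Cox proportional hazards model, if a sufficient number of events will be observed". Group differences are then given as hazard ratios with 95% intervals and p-values.

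Only the third is a comparison between arms, and only the third has an interval attached.

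On size, Section 11.7 says "Targeting a total of at least 80 evaluable patients, we aim to recruit about 100 patients". The amendment overview in Section 18.1 gives 400 as the initial plan and adds that "111 patients have been randomized into the study until the trial has been set on-hold on June 11, 2021". Its list of changes has no entry for Section 11.5, and its entry for Sections 11.2 and 11.3 says that analyses of the other endpoints stay as first planned.

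**The concern.** A hazard ratio needs events in both arms. If one arm has none, the estimate is zero or infinite; if neither has any, it is undefined. A rule written for 400 patients was carried over to a trial about a quarter of that size, and the endpoint it serves is expected to be uncommon.

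At stake is whether the comparative safety objective gets an answer. If the Cox model is not run, or gives no finite ratio, the protocol specifies no effect measure and no interval for major bleeding between a therapeutic-dose arm and a prophylactic-dose arm. Any difference that a reader then forms from the percentages is post hoc. The decision to run the comparison is also taken on observed event counts in an open-label trial.

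**Working it through.** **Inputs from the protocol.** About 100 patients, 1:1, so 50 per arm (Sections 11.7 and 5). With 111 randomized, 111/2 is about 55 per arm. No sample size, event count, power or expected rate is stated for bleeding.

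**The plan's own figure.** The stated size concerns D-dimer and reproduces. Residual SD = 0.8 × √(1 − 0.5²) = 0.693. For a difference of 0.44 at two-sided 0.05 and 80% power this gives 39 per group; at 40 per group the power is 80.1% (t-based). It is not in dispute, and it does not bear on bleeding.

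**Assumption.** Day-35 major-bleeding risks between 0.5% and 10% per arm. The protocol's hints point different ways. Section 1.2 says of an earlier post-discharge rivaroxaban trial "The incidence of major bleeding in both study arms was low", but reports that another earlier trial in acutely ill medical patients failed mainly because of bleeding. Section 15.1 expects a risk similar to that of the age-adjusted population, with pulmonary hemorrhage in some cases.

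**Chance that the hazard ratio does not exist.** With n per arm and risks p₁ (rivaroxaban) and p₀ (standard of care):

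P(at least one arm without an event) = 1 − [1 − (1−p₁)ⁿ][1 − (1−p₀)ⁿ]

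Example, 2% in both arms, n = 50: 0.98⁵⁰ = 0.364, so 1 − (1 − 0.364)² = 0.60.

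| Risk, rivaroxaban / standard of care | Expected events (50 per arm) | At least one empty arm, 50 per arm | At least one empty arm, 55 per arm |
|---|---|---|---|
| 0.5% / 0.5% | 0.5 | 95% | 94% |
| 1% / 1% | 1.0 | 84% | 82% |
| 2% / 1% | 1.5 | 75% | 72% |
| 2% / 2% | 2.0 | 60% | 55% |
| 4% / 2% | 3.0 | 45% | 40% |
| 4% / 4% | 4.0 | 24% | 20% |
| 5% / 5% | 5.0 | 15% | 12% |
| 10% / 5% | 7.5 | 8% | 6% |

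With equal risks the probability is one half when (1−p)ⁿ = 1 − √0.5 = 0.293. That gives p = 1 − 0.293^(1/50) = 2.4%, or 2.2% with 55 per arm.

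**Precision when it does exist.** With D events, the standard error of the log hazard ratio is about 2/√D, so the 95% interval is the estimate multiplied and divided by exp(1.96 × 2/√D). This is 16-fold for D = 2, 7.1-fold for D = 4, 5.0-fold for D = 6 and 3.5-fold for D = 10. By the Schoenfeld formula, D = 4(1.96 + 0.84)²/(ln HR)², 80% power needs 66 events for a ratio of 2 and 27 for a ratio of 3.

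**What a low count leaves open.** For 0/n the exact two-sided 95% upper limit is 1 − 0.025^(1/n): 7.1% for 0/50 and 6.5% for 0/55. If the true rivaroxaban risk were 2%, no bleed in 50 would still occur with probability 0.98⁵⁰ = 36%.

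**What a score interval gives.** Newcombe 95% intervals for the risk difference, in percentage points, 50 per arm, rivaroxaban count first:

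| Events | Difference | 95% interval |
|---|---|---|
| 0 v 0 | 0 | −7.1 to +7.1 |
| 1 v 0 | +2 | −5.3 to +10.5 |
| 2 v 0 | +4 | −3.7 to +13.5 |
| 3 v 0 | +6 | −2.1 to +16.2 |
| 3 v 1 | +4 | −5.4 to +14.3 |

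Each is finite, including 0 v 0.

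**The case against.** The strongest reply is that Section 11 sets out principles and leaves detail to an analysis plan that is not shown. A numerical threshold for enough events, or a sparse-data fallback, is usual content there. This stands as far as the missing threshold goes, and that absence is not counted here. It does not cover the choice of measure: the protocol itself makes the hazard ratio the expression of group differences and itself makes it conditional.

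Secondly, the condition is a sensible guard against printing a zero or infinite ratio, it refers to a number of events and not to a difference between arms, and bleeding is classified by an independent committee. All fair. The guard is sound; what is missing is a comparison that survives when it operates.

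Two stronger readings are tempting. A reader might infer that bleeding would be left without any usable result. The document does not support that: percentages by arm and Aalen-Johansen incidence do not depend on the event count, and a crude difference can be formed from them. Nor is the Cox model shown to fail for all bleeding. Clinically relevant non-major bleeding is defined broadly in Section 9.3.1 and may supply enough events; at 10% v 5% an empty arm has only an 8% chance. A reader might also infer that the plan would treat an absence of bleeds as evidence of safety. It nowhere says so: the analyses are called explorative, and benefit-risk is only to be explored (Section 9.4). The valid statement is narrower: no bleed in 50 patients leaves risks up to about 7% open, and no stated output would show this.

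Finally, crude proportions treat every patient's day-35 status as known, yet Section 10.3 withdraws patients who lose the ability to consent, for example on intubation. This objection holds, and the fix has to deal with it.

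**Conclusion.** The point holds for major bleeding and is worth acting on. The only between-arm measure that the protocol states for its principal safety endpoint is one that, at 50 to 55 patients per arm, will more likely than not be inestimable if the risk is about 2% or less in each arm. The probability is 55% to 60% at 2%/2% and 82% to 84% at 1%/1%. These figures rest on assumed risks, since the protocol gives none. From about 4% v 2% upward an empty arm is no longer the likelier outcome (45% at 50 per arm), and the weakness becomes one of precision, with intervals about 7-fold each way at 4 events and 5-fold at 6. Across the assumed range, the stated objective of comparing major bleeding is poorly served by the stated measure, and no other between-arm contrast with an interval is specified. The explorative label strengthens the case, since such a study depends on estimates and their intervals.

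**What to change.** In Section 11.5 and the Synopsis, make the main bleeding comparison the between-arm difference in the risk of ISTH major bleeding up to day 35 in the safety set, with a 95% score-based interval (Newcombe or Miettinen-Nurminen), reported whatever the number of events. Do the same for clinically relevant non-major bleeding.

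State how patients who die without a major bleed, and those who leave the study before day 35, count in this difference. Section 11.1 treats study discontinuation as independent censoring for time-to-event endpoints, while Section 11.5 lists it as a competing event, so the rule has to be explicit. Show the day-35 Aalen-Johansen estimates for each arm alongside.

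Keep the Cox hazard ratio as a supplement, shown when both arms have events.

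The cost is a sentence in two places and a few table rows, with no new data. The interval will be wide (−7.1 to +7.1 points if neither arm of 50 has an event), which is an accurate account of what about 100 patients can show.

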### **Safety Endpoints**

Safety analyses will follow standard procedures for the reporting of adverse events; these will be reported as frequencies (percentages) by treatment group. All safety analyses will be based on the safety set. One safety endpoint of particular interest are bleeding events (see Section 9.3.1). The time to bleeding events will be analyzed in a Cox proportional hazards model, if a sufficient number of events will be observed. Treatment group differences will be reported as hazard ratios with 95% confidence intervals and p-values testing the null hypothesis of no group difference (i.e. HR=1). The estimation of the probability for bleeding events will account for competing events such as death and premature study discontinuation using the Aalen-Johansen estimator, the so-called cumulative incidence function.

Differences between treatment groups in continuous laboratory parameters and vital signs over follow-up time will be explored in longitudinal box plots.

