### 11.1 Definition of populations included in the analyses

The primary efficacy analysis as well as all secondary efficacy analyses will be based on the full analysis set (FAS) following the intention-to-treat principle and will include all randomized patients. Safety analyses will be based on the safety set (SAF) including all randomized patients with at least one dose of study medication or at least one dose of SOC (UFH or LMWH).

For time-to-event endpoints, study discontinuations will be dealt with as independent right censoring. Patients discontinuing study drug will be follow up for endpoints. Otherwise missing values will be dealt with using multiple imputation methods. If, against expectations, the proportion of patients with premature study discontinuations is substantial, shared random effects models simultaneously modelling time to primary outcome and time to study discontinuation will be used to explore the robustness of the treatment effect.

Sensitivity analyses will be performed in all patients (a) completing at least 7 days of treatment and (b) completing the study adherent to the study protocol. These will be referred to as the (a) while on treatment population and (b) per-protocol (PP) population.

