### 11.3 Secondary Efficacy Endpoint

The secondary combined endpoint includes

Time to first event of either

- Venous thromboembolism (VTE) (deep venous thrombosis (DVT) and/or fatal or non-fatal pulmonary embolism (PE))
- Arterial thromboembolism
- New myocardial infarction (MI)
- Non-hemorrhagic stroke
- All-cause death
- Progression to intubation and invasive ventilation

Time to first event of either of the components of the secondary composite endpoint will be analyzed using a Cox proportional hazards regression model with treatment and the stratification variables of the randomization (site, gender (male, female, diverse), age (< 65 versus  $\geq$  65 years), kidney function (eGFR  $\geq$  30 mL/min/1.73m^2 and < 50 mL/min/1.73m^2 versus eGFR  $\geq$  50 mL/min/1.73m^2), history of CAD or heart failure (yes/no), oxygen demand on admission to the hospital (supplementary oxygen required versus not required), setting (outpatients versus hospitalized patients)) as factors. The treatment effect will be reported as hazard ratio (HR) with 95% confidence interval and p-value for the null hypothesis H0: HR=1. The primary endpoint will be visualized as Kaplan-Meier curves. Sensitivity analyses will explore the robustness of these analyses.

The analyses of the time-to-event outcomes among the secondary endpoints (such as time to VTE, time to arterial thromboembolism, time to new MI, time to non-hemorrhagic stroke, time to all-cause death, time to progression to intubation and invasive ventilation) will follow the same lines as the analysis of the composite outcome, i.e. survival analyses comprising Cox proportional hazard regression models and Kaplan-Meier curves. Death will be treated as a competing event except when analyzing all-cause death, naturally.

Longitudinal D-dimer measurements assessed at day 7, 35 and 60 will be analyzed on the logarithmic scale using a mixed model for repeated measures (MMRM) approach. The model will include treatment, visit, treatment-by-visit interaction and stratification variables of the randomization as factors as well as logarithmic D-dimer baseline value as covariate. The residuals will be assumed to follow a multivariate normal distribution with unstructured covariance matrix. LS means of the group means and their differences will be computed for the various timepoints and reported with 95% confidence intervals.

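### The Aalen-Johansen bleeding estimate counts study discontinuation as a competing event, which contradicts the plan's own censoring rule and lowers the estimated day-35 bleeding risk

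*Protocol*

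**What the plan says.** Section 11.5 of the protocol plans two time-to-event analyses of bleeding. The first is a regression: "The time to bleeding events will be analyzed in a Cox proportional hazards model, if a sufficient number of events will be observed". The second is a cumulative incidence curve: "The estimation of the probability for bleeding events will account for competing events such as death and premature study discontinuation using the Aalen-Johansen estimator". The safety part of the synopsis has the same wording on "competing events such as death and premature study discontinuation using the Aalen-Johansen estimator".

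Section 11.1 and its counterpart in the synopsis set a general rule: "For time-to-event endpoints, study discontinuations will be dealt with as independent right censoring". Section 11.1 also separates leaving the study from stopping the drug: "Patients discontinuing study drug will be follow up for endpoints". The conflict therefore concerns departure from the study only.

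For the components of the secondary composite, section 11.3 names one competing event: "Death will be treated as a competing event except when analyzing all-cause death, naturally".

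Section 2.1 sets the target for safety as bleeding outcomes up to day 35. Fatal or non-fatal major bleeding is the principal safety endpoint (section 9.3.1).

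**The concern.** A competing event is one after which the event of interest can no longer happen. Death qualifies. Study discontinuation does not, and the protocol treats it accordingly elsewhere: section 10.1 asks for outcomes on every randomized subject, and section 10.3 has outcomes collected at day 35 after withdrawal of consent or loss to follow-up.

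When discontinuation is entered as a competing event, each patient who leaves without a bleed stays in the denominator as someone who can never bleed. The curve then estimates the probability of a bleed observed before death or study exit. That is a different quantity from bleeding risk up to day 35, and it cannot be larger.

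Two things are at stake. The absolute bleeding risk comes out too low, which is the unfavourable direction of error when an initially therapeutic regimen is compared with a prophylactic one. And if the arms lose patients at different rates, the arm that loses more shows a lower curve for that reason alone.

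**Working it through.** **Inputs.** The horizon is 35 days (section 2.1). The protocol states no bleeding, death or discontinuation rate, so there is no figure of its own to reproduce. Everything below rests on assumed rates: net 35-day bleeding 10%, net 35-day death 5%, discontinuation 5% to 30%, constant hazards, and discontinuation independent of bleeding.

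**Formula.** Cumulative hazards over 35 days:

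- bleeding: B = −ln(0.90) = 0.1054
- death: D = −ln(0.95) = 0.0513
- discontinuation at proportion c: C = −ln(1 − c)

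With discontinuation competing, the day-35 cumulative incidence is B/(B+D+C) × [1 − exp(−(B+D+C))]. With discontinuation censored and death still competing, set C = 0.

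**Censored, as in section 11.1.** 0.1054/0.1567 × (1 − 0.90×0.95) = 0.6726 × 0.145 = 9.75%.

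**Competing, as in section 11.5, at 20% discontinuation.** C = 0.2231, so 0.1054/0.3798 × (1 − 0.855×0.80) = 0.2774 × 0.316 = 8.77%.

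| Discontinuation | Competing, constant hazards | Relative shortfall from 9.75% | Competing, all discontinuation at the start, 9.75% × (1 − c) |
|---|---|---|---|
| 5% | 9.51% | 2.5% | 9.26% |
| 10% | 9.27% | 5.0% | 8.78% |
| 20% | 8.77% | 10.1% | 7.80% |
| 30% | 8.24% | 15.5% | 6.83% |

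Under constant hazards the relative shortfall is about half the discontinuation share. If all discontinuation happens at the start, it equals that share. Net bleeding of 5% or 20% gives nearly the same relative figures: at 20% discontinuation, 10.2% and 9.9%. A simulation of 2,000,000 patients at 10% bleeding, 5% death and 20% discontinuation gave 9.80% censored and 8.80% competing, within 0.05 points of the formula.

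**Unequal discontinuation, for illustration.** With identical bleeding and death hazards in both arms, and discontinuation of 30% in one and 10% in the other, the curves end at 8.24% and 9.27%. This is a difference of 1.0 point with no true difference behind it.

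**Hazard ratio.** In the cause-specific Cox model a patient leaves the risk set at study exit whether the exit is labelled censoring or a competing event. The partial likelihood is the same, and so are the hazard ratio, its interval and its p-value.

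**The case against.** The strongest reply has four parts.

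*The treatment comparison does not move.* This is correct. A reader might infer that the between-arm bleeding test is biased; it is not, because section 11.5 bases it on the Cox hazard ratio. The defect is confined to the cumulative incidence estimate. Still, the Cox model is conditional on enough events, and with about 100 patients it may not be run. The curve could then be the only time-to-event result for bleeding.

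*The size may be small.* This is also fair. Section 11.1 calls substantial study discontinuation contrary to expectation, and the 80 evaluable of about 100 recruited in section 11.7 is not a dropout rate. At 5% to 10% discontinuation the shortfall is 0.24 to 0.48 points (9.75 − 9.51 and 9.75 − 9.27). With about 50 patients per arm, a 10% risk has a standard error of √(0.10×0.90/50) = 4.2 points, so even the shift of about 1 point at 20% is roughly a quarter of a standard error. Nor do the documents show that the arms will differ in discontinuation. The 30% versus 10% case is hypothetical.

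*The quantity is legitimate.* Bleeding observed before death or study exit is a valid estimand, but the protocol does not name it as its aim. It also adds little: with no other censoring before day 35, this Aalen-Johansen estimate reduces to the crude proportion with a bleed, close to the percentages already planned for adverse events.

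*Censoring is an assumption too.* This stands. Section 10.3 withdraws patients who lose the ability to consent, for example at intubation, and that is unlikely to be unrelated to bleeding risk. It calls for a sensitivity analysis. It does not justify treating these patients as unable to bleed.

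A reader might also see a mirror-image error in section 11.3, because it plans "survival analyses comprising Cox proportional hazard regression models and Kaplan-Meier curves" for components such as VTE and MI. The text does not support that as a separate error. The same paragraph declares death a competing event for those components, so it is at most unclear how the curves will be drawn.

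**Conclusion.** The point holds as an internal contradiction with a known direction. Two current passages, each repeated in the synopsis, handle the same departures in incompatible ways, and the version in section 11.5 lowers the estimated day-35 bleeding probability. The direction follows from the definition of the estimator. The size rests on assumed rates: under 10% bleeding, 5% death, constant hazards and independent discontinuation it is 2.5% to 15.5% relative for discontinuation of 5% to 30%, and at most the discontinuation share itself. The lower end is more in keeping with what the protocol expects.

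The finding does not extend to the Cox hazard ratio, to the efficacy components in section 11.3, or to any claim that one arm will in fact look safer. That the study is exploratory limits the consequences, but it does not resolve which of the two rules applies to the principal safety endpoint.

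**What to change.** In section 11.5 and the matching synopsis paragraph, remove premature study discontinuation from the competing events. Keep death as the competing event, and state that patients are censored at study discontinuation, as section 11.1 and the synopsis already require.

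Add one sensitivity analysis for informative discontinuation in the bleeding estimate, with explicit attention to withdrawal at loss of the ability to consent (section 10.3). The joint modelling that section 11.1 holds in reserve is written for the primary outcome and does not cover bleeding.

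The cost is one phrase in two places, the same estimator and software, and one extra analysis. The reported bleeding risk becomes slightly less favourable.
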